i. Study Design: This randomized controlled study will assign approximately 200 subjects (100 each) to the following arms (Appendix 1): 1) High protein diet group based on 1 gram of protein per pound of lean body mass, and 2) Standard protein diet group as control based on 0.5 gram protein per pound of lean body mass with same calories. All participants will meet with a registered dietitian, physician or nurse practitioner to assist them with their diet efforts in all the arms. In the study, the percent energy from fat will be held constant at 30% and the differences in the diets relate only to the protein and carbohydrate contents (30% protein and 40% carbohydrate, and 15% protein and 55% carbohydrate respectively). At the initial visit patient will not be calorie restricted but will have standardization of their nutritional macronutrient intake based on their group randomization. At the 2 week visit patient will then begin a 1500 calorie restricted diet with the same macronutrient composition (ie. 30% protein and 40% carbohydrate, and 15% protein and 55% carbohydrate respectively for the high and standard protein groups).

ii. Number of Subjects: Approximately 200 healthy volunteers age 30 years and older with a BMI between 27 to 40 kg/m² will be able to take part in this study.

iii. Estimated Study Duration: Accrual period is 3-4 years; anticipated dropout rate is 20%; and total study duration is approximately 5 years (taking into account data analysis).

iv. Subject Eligibility: Subjects will be assigned an enrollment number after signing the informed consent form. The subjects will complete all the screening tests and procedures as listed. When a subject completes the screening tests and procedures, the subjects will be assigned a randomization number. Subjects will be randomized into one of the two diet groups as described in Appendix 1.

The practitioner at screening will obtain each subject's date of birth, sex, race, medical history, current medications, and smoking and alcohol history. The physician will perform complete physical examinations. Height will be measured using a standardized stadiometer, while the subject stands

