Stool samples will be collected on day 3, 7, 14, 17, 21, 28, 42, 56, 84 and 112. Subjects will be provided with kits for home sampling. The subjects will urinate first then defecate into the Fisherbrand Commode Specimen Collection System. Subjects will use a spoon to transfer freshly defecated feces to a Para-Pak stool collection cup prefilled with 95% ethanol to fix the samples, allowing storage at room temperature for up to 2 weeks. The remaining feces will be frozen. This involves removing the cup from the toilet hat, tightly closing the lid, and transferring the cup to a Ziploc bag for storage in the subject's freezer. Frozen samples will be delivered to the VA clinic during scheduled study visits using a Styrofoam box and frozen packs. Subjects who forget to bring samples will be provided with prepaid envelopes to mail their samples to the coordinator. Samples will be stored at -80°C. Ethanol-fixed and fresh frozen samples give comparable metagenomics results to samples stored in preservatives such as RNALater while minimizing subjects' risk of exposure to toxic chemicals ⁽³³⁾.

Statistical Analysis:

Statistical Design: This is a 2-group randomized nutritional study to evaluate whether the high-protein diet will improve weight loss in comparison to a standard (control) diet. Eligible subjects will be randomly assigned into one of the two groups in a ratio of 1:1.

Sample Size Determination: The sample size is determined based on the Specific Aim 1 to significantly improve weight loss, as observed by comparing the high-protein diet to the standard diet. The primary outcome of interest is weight loss at 16 weeks (the end of the study). An evaluable sample size of at least 165 (i.e., 55 per arm) will achieve 80% power to detect an effect size of 0.245 using an F test with a two-sided 0.05 significance level when comparing each of the two high-protein diets to the standard diet, assuming that the mean weight loss for the standard diet is 14 lbs with the common standard deviation within group of 10 (from preliminary data), and the size of the variation in the means is 2.45. To account for an attrition rate of up to 20%, we will enroll a total of 200 subjects (66 per arm). Preliminary data suggest that the estimated effect size ranges from 0.23-0.34 when comparing the high-protein diet to the standard diet.

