two groups. The data for all time points will then be fitted to a multivariate model under a negative binomial distribution using DESeq2 with diet group, time point, interaction between diet and time point, baseline BMI, age, sex, and smoking status as covariates. This model will be compared to a reduced model that does not include the diet:time point interaction⁽⁷⁰⁾. A likelihood ratio test will be used to identify microbes with differential abundance by diet at time points after baseline. Estimates of significance will be adjusted for multiple hypothesis testing⁽⁷¹⁾. OTUs that are differentially abundant on a HPD will be grouped by hierarchical clustering, which we anticipate will highlight distinct kinetic patterns of microbial change.

Expected results/potential pitfalls: We do not anticipate problems with the collection or transportation of fecal samples to our clinical research unit. We predict that *Akkermansia* will significantly increase on a HPD as was seen in our rodent studies. We further predict that most HPD-responsive microbes will have altered abundance within the first 3 to 7 days as has been observed in other dietary studies^(72,73). We estimate a 20% dropout rate based on our high protein meal replacement study, leaving approximately 80 subjects per group. This compares favorably to published studies reporting dietary effects on the microbiome using sample sizes of 10-15^(72,73,74). We anticipate that a HPD will have a similar magnitude of effect as these previously studied diets and hence we expect to have sufficient numbers to detect compositional differences.

2.2 Identification of metagenes affected by a high protein diet.

Experimental protocol: We will assess the functional consequences of altered microbial composition by sequencing the genes carried by intestinal microbes. Shotgun sequencing of DNA extracted from fecal samples will be performed using the HiSeq 3000 with a target depth of 10 GB data per sample, comparable to the 11.7 GB depth used by the Human Microbiome Project for stool samples⁽⁷⁵⁾. Due to the costs of sequencing at this depth, we will only sequence baseline samples and samples from day 112.

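### Enrolling 200 does not keep the stated minimum of 165 evaluable subjects at 20% attrition; it leaves 160, though this does not show the two-arm trial to be underpowered

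*Combined protocol and SAP*

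**What the plan says.** All references are to the combined protocol and SAP, section 4 (Work Proposed) unless noted.

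- **Aim 1, Sample Size Determination, evaluable number:** "An evaluable sample size of at least 165 (i.e., 55 per arm) will achieve 80% power". The test is specified as "using an F test with a two-sided 0.05 significance level", with an effect size of 0.245. The inputs are a "common standard deviation within group of 10 (from preliminary data), and the size of the variation in the means is 2.45". The comparison is described as two high-protein diets, each against the standard diet.
- **Same paragraph, enrolment:** "To account for an attrition rate of up to 20%, we will enroll a total of 200 subjects (66 per arm").
- **Aim 1, Estimated Study Duration:** "anticipated dropout rate is 20" per cent. Here 20% is the expected rate, whereas the sample-size paragraph treats it as an upper limit.
- **Aim 1, Study Design and Statistical Design:** two groups, allocated 1:1, about 200 subjects, 100 in each.
- **Aim 2.1, Expected results:** the same 20% dropout is applied to the same cohort, "leaving approximately 80 subjects per group". Aim 2.2 repeats 80 per group as the estimated final sample.
- **Human Subjects, Risk to Subjects:** about 198 volunteers rather than 200.

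**The concern.** An attrition allowance has one job: after the allowed losses, the number left must be no smaller than the number the power calculation requires. Here the required number and the enrolment target stand in consecutive sentences, and the second does not deliver the first at the attrition rate it names. The Aim 2 section works out the number remaining and gets a figure below the Aim 1 minimum without remarking on it.

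At stake is whether the primary sample-size justification can be relied on as written. A method that multiplies by (1 + d) falls short for any number of arms. At d = 0.20 it returns 1.2n x 0.8 = 0.96n, which is 4% under the requirement. If the calculation is redone for two arms and the same step is reused, the shortfall carries over.

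**Working it through.** **Inputs.** Evaluable minimum 165 (55 per arm), enrolment 200 (66 per arm), attrition 20%, SD 10 lbs, variation in the means 2.45, alpha 0.05 and power 80%, all from Sample Size Determination. Two arms of 100, from Study Design. 80 per group after dropout, from Aim 2.1. 198 volunteers, from Human Subjects.

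**1. Reproduce the evaluable number.** The effect size is 2.45/10 = 0.245, which has the form of Cohen's f. For a one-way F test with k groups and N subjects in total, the noncentrality parameter is N x f² and the degrees of freedom are k - 1 and N - k. With k = 3:

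| N (per arm) | Noncentrality | Power |
|---|---|---|
| 165 (55) | 165 x 0.060025 = 9.90 | 80.4% |
| 162 (54) | 162 x 0.060025 = 9.72 | 79.6% |

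So 55 per arm is the smallest whole number that reaches 80%. The 165 reproduces, as a three-arm total.

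**2. Reproduce the enrolment number.** Multiplying by 1.2 gives 55 x 1.2 = 66 and 165 x 1.2 = 198. The first matches the stated per-arm figure exactly. The second matches the Human Subjects figure exactly and rounds to 200. Dividing by 0.8 gives 55/0.8 = 68.75, or 69 per arm, and 165/0.8 = 206.25; three arms of 69 make 207. The stated figures fit the first method and not the second.

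**3. Apply the stated attrition to the stated enrolment.**

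- 200 x 0.8 = 160, which is 5 below 165
- 66 x 0.8 = 52.8 per arm, below 55
- 80 per group x 2 groups = 160, the Aim 2.1 figure
- Attrition at which 165 is just kept: 1 - 165/200 = 17.5% for 200 enrolled, or 1 - 165/198 = 16.7% for 198

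**4. Cost in power on the paragraph's own three-group test.** At N = 160 the noncentrality is 9.60 and power is 79.1%, a fall of 1.3 points from 80.4%. Starting from 198 enrolled, 158.4 remain and power is 78.6%.

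**5. The same check for the two-arm trial described.** With two equal groups, f is half the difference divided by the SD, so f = 0.245 with SD 10 means a difference of 2 x 0.245 x 10 = 4.9 lbs.

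| Reading of the effect size | N evaluable | Power |
|---|---|---|
| Cohen's f = 0.245 (4.9 lbs) | 134 (67 per arm) | 80.4% |
| Cohen's f = 0.245 (4.9 lbs) | 160 (80 per arm) | 86.9% |
| Cohen's f = 0.23, low end of the stated range | 160 | 82.4% |
| Standardised mean difference 0.245 (2.45 lbs) | 160 | 33.8% |
| Standardised mean difference 0.245 (2.45 lbs) | 165 | 34.6% |

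On neither reading do the five missing subjects decide whether 80% is reached.

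**The case against.** The strongest objection is that the shortfall of five depends on a total that does not belong to this trial. The 165 is 3 x 55, left in a protocol that randomises two groups. Against the per-arm minimum of 55, 100 per arm less 20% leaves 80, with plenty to spare. Enrolment is also described as approximate, and in the sample-size paragraph 20% is an upper limit. A change of 1.3 points, in a calculation that has to be replaced anyway, is slight.

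Most of this stands, and it limits the consequence. It does not remove the inconsistency. The paragraph states a minimum evaluable number and a maximum attrition, and both cannot hold at 200. Nor is 20% only a worst case, because the study-duration item gives it as the expected rate. The wrong inflation step would also survive a change in the number of arms: for the two-arm requirement of 134, 134 x 1.2 = 160.8, or 161 enrolled, and 161 x 0.8 = 128.8, below 134.

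A reader might infer that the trial will miss 80% power at the attrition it expects, or that enrolment must rise to 207. The documents support neither. Both inferences apply a three-arm requirement to a two-arm trial; with f = 0.245, two arms give 86.9% at 160. It would be equally unsafe to call the power adequate without qualification, since the paragraph never states the target difference in pounds.

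**Conclusion.** The stated figures are inconsistent: 200 enrolled with 20% attrition gives 160 evaluable, not the minimum of 165. That rests on arithmetic alone and is confirmed by the protocol's own 80 per group. The cause, multiplying by 1.2 where division by 0.8 was needed, is an inference because the working is not shown, but 66 and 198 both match it exactly.

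The size is small: 5 subjects, and 1.3 points of power on the three-group F test that the paragraph uses. This error does not show that the two-arm trial is underpowered. That conclusion assumes 0.245 is Cohen's f, as 2.45/10 suggests. If it were a standardised mean difference, power would be about 34% at 160, but it would be about 35% at 165 too, and the fault would lie in the assumed effect rather than in the attrition allowance.

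**What to change.** In Sample Size Determination:

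- Replace 165 (55 per arm) and 200 (66 per arm) with two-arm figures: 200 enrolled (100 per arm) and 160 evaluable (80 per arm) at 20% attrition.
- State the power of the two-arm comparison at 160 for an explicit difference in pounds. If 0.245 is confirmed as Cohen's f, that difference is 4.9 lbs with SD 10, and the power is 86.9%.
- Compute any attrition inflation as n/(1 - 0.20).

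In Human Subjects, bring the 198 into line with the enrolment figure used elsewhere.

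Quoting three-group power at 160, or declaring a 17.5% attrition tolerance, would not be a sufficient repair, because both keep the three-arm base. The cost is a few sentences of text. No added enrolment is needed, and neither the design nor the conduct of the trial changes.

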The objectives of this proposal, accordingly, are to corroborate data from our preliminary human studies showing that a high protein diet results in body weight loss. We will correlate the observed clinical findings with an understanding of normal and pathological appetite regulatory mechanisms in experimental animals. In order to accomplish the stated goals of this program, we have brought together interdisciplinary collaborations at our VA Medical Center from diverse backgrounds including: microbiome, cell biology, molecular biology, neurophysiology and human clinical investigations, including health services research to investigate the mechanisms regulating feeding behavior and obesity. Our proposal is focused on addressing three hypotheses linking clinical and translational approaches that are critical to understanding the pathophysiology of satiety/obesity.

1. A higher protein replacement diet will result in early satiety signaling and weight loss in obese patients and a differential pattern of postprandial GI hormone release.
2. Patients on the high protein diet will have shifts in the composition and function of their intestinal microbiome.
3. Abundance of specific fecal microbes can be used to predict response to a high protein diet.

C. Specific Objectives.

AIM 1: To Confirm the Hypothesis that a High Protein Diet Reduces Body Weight and Alters the Pattern of Postprandial Gut Hormone Release in Obese Patients.

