Rationale: In the first aim, we will evaluate whether an isocaloric high protein diets (1 gram of protein per pound of lean body mass) will improve weight loss in comparison to a standard protein diet based on 0.5 gram of protein per pound of lean body mass. Our preliminary studies support the concept that a higher protein meal replacement will result in significant losses of body mass in obese subjects and that a high endogenous level of ghrelin in patients with neuroendocrine tumors results in increased weight gain. In the study, bioelectrical impedance will be used to determine the protein requirement at the level of 0.5 or 1 gram per pound of lean body mass. Weight loss will be the primary outcome. A secondary variable will include satiation as measured using a standard questionnaire, liver stiffness as determined by transient elastography, and microbiome changes determined by 16S sequencing. In addition, we will establish the changes in the levels of the orexigenic peptide ghrelin including the ratio of ghrelin to des-acyl ghrelin, and anorexigenic peptides PYY, leptin, CCK, GLP-1 and nesfatin-1 following high protein meal ingestion.

AIM 2. Characterize the changes in the fecal microbiome induced by a high protein diet

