i. Ghrelin: Isolated in 1999, ghrelin is an orexigenic peptide hormone secreted mainly by the X/A-like cells of the gastric fundus and is the endogenous ligand of the growth hormone secretagogue receptor (GHS-R).⁽⁴⁶⁾ In humans, plasma ghrelin levels rise prior to meals and fall after eating.⁽⁴⁷⁾ Ghrelin has been implicated in both mealtime hunger and the long-term regulation of body weight. Levels are known to negatively correlate with body mass index (BMI) so that levels are increased in both obese patients who have lost weight through dietary restriction and patients with anorexia nervosa.⁽⁴⁸⁾ Also, patients who have lost weight secondary to gastric bypass surgery have suppressed ghrelin levels. Not only are the levels lower than in those patients who have lost weight by nonsurgical means, but also the meal-related fluctuations and diurnal rhythm are not found after gastric bypass surgery.⁽⁴⁹⁾ There is also a clear negative association between ghrelin and insulin secretion.^(47,50) In the rat as in humans, ghrelin is principally synthesized in X/A-like cells in the oxytic mucosa of the fundus.⁽⁴⁶⁾ The major forms of ghrelin include acylated ghrelin, in which serine-3 is octanoylated (a unique biological finding), and non-acylated ghrelin.⁽³⁾ In blood, non-acylated ghrelin circulates in far greater amounts, accounting for more than 90% of total ghrelin.⁽¹⁰⁾ In rodents, we have shown that the stimulatory action of ghrelin on food intake is linked with the activation of neuropeptide Y (NPY) synthesizing neurons⁽¹⁰⁾ in the arcuate nucleus (Arc) that projects to the paraventricular nucleus of the hypothalamus (PVN) and lateral hypothalamic areas. Both of these hypothalamic nuclei regulate feeding behavior and energy balance. In this way, ghrelin is thought to serve as the missing link between enteric nutrition and central regulation of energy balance.⁽³⁾ Recently we also established that non-acylated ghrelin can counteract the orexigenic action of ghrelin in rats⁽⁵¹⁾ but showed that obestatin, a newly identified ghrelin associated peptide (GAP) that is putatively derived from post-translational processing of the prepro-ghrelin gene, did not influence food intake contrary to the initial claim.⁽⁵²⁾

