ii. Glucagon-like Peptide-1 (GLP-1), Peptide YY (PYY), and Leptin: are also hormones involved in satiety.^(8,12) The effects of a high protein diet on the regulation of these GI hormones has been little investigated.⁽⁵⁵⁾ Leptin is secreted directly from adipose cells in proportion to their metabolic activity. Insulin is secreted from pancreatic beta cells in response to increases of circulating glucose. Leptin and insulin are increased in direct proportion to the amount of body fat. Insulin and leptin are both transported through the blood-brain barrier and influence food intake and body weight. When the action of either leptin or insulin is reduced locally within the brain, subjects consume more food.^(55, 56) Recently, evidence has emerged that insulin and leptin activate the same intracellular pathways in neurons in the Arc and that they interact to reduce food intake and body weight.^(56,67) GLP-1 is secreted in a nutrient-dependent manner in humans *via* either direct interaction of luminal contents with the L cells or indirectly *via* a proximal-distal loop mechanism⁽⁵⁸⁾ The processing of proglucagon is different in the pancreas and the intestine; the pancreas contains mainly GLP-1 (1-36) amide or GLP-1 (1-36)-gly, while the intestine contains mainly GLP-1 (7-36) amide and GLP-1 (7-36) gly.⁽⁵⁹⁾ The major circulating forms in humans are the intestinal forms, GLP-1 (7-36) amide (henceforth GLP-1) and GLP-1 (7-36)-gly, and these forms have similar potency for stimulation of insulin and glucagon secretion.⁽⁵⁹⁾ The secretion profile for GLP-1 is biphasic with an early peak at 30 min after nutrient ingestion (indirect stimulation of lower bowel by signals from

upper gut) followed by a more prolonged peak (direct stimulation of lower bowel by luminal contents) for 1-2 h after the meal.^(60,61) One recent study indicates that plasma levels of GLP-1 are enhanced by high protein diet in obese humans.⁽⁶²⁾ In addition, several reports have shown that GLP-1, infused peripherally in normal human subjects, increased satiety and reduced food intake.^(63,64) Similar results were observed in type II diabetic patients.^(65,66)

Microbiome Changes Associated with Obesity, Weight Loss and High Protein Diet

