erect with feet together and head level; height will be measured to the nearest 0.5 cm. Weight will be measured to the nearest 0.25 lbs using a balanced scale. BM will be calculated as weight in kilograms divided by the square of the height in meter. Waist and hip circumferences will be measured in the standing position. The subject should be wearing unrestricting undergarments with a hospital gown being optional. Waist circumference will be measured at the level midway between the lateral lower rib margin and the iliac crest. Hip circumference will be measured at the level of the trochanters through the pubic symphysis.

v. Study Visits: Participants in both groups will meet with registered dietitians every 2 to 4 week throughout the Intervention Phase and the dietary intake patterns will be reviewed. A variety of visual tools including food models and common household measuring utensils will be used during the interview to help participants gauge amounts accurately.

a. Assessment will be performed at weeks 0, 2, 4, 6, 8, 12, 16.

1. Vital signs
2. Height
3. Weight
4. Vital Signs
5. Fasting Labs: CBC/Metabolic Panel, Hemoglobin alc, TSH, Cholesterol, TG, HDL, blood sugar, hormone panel (leptin, CCK, GLP-1, PYY, ghrelin, insulin, nesfatin-1)
6. Body Composition and estimated resting metabolic rate
7. Hepatic transient elastography
8. Stool collection for fecal short chain fatty acids and microbiome analysis
9. Satiety Scale
10. 3-Day food record
11. Food frequency questionnaire
12. Adverse Event Tracking

Compliance with consumption will be assessed using check lists that will be turned in during clinical visits. Minimal accepted compliance will be set at 80% of the assigned diet. A participant will be withdrawn once cumulative consumption levels fall to the point that 100% compliance cannot get them over the 80% threshold by the final day of the intervention.

Study Schedule

Procedures	Screen Week -1	Baseline Week 0	Week 2	Week 4	Week 6	Week 8	Week 12	Week 16
Informed Consent	X							
Medical History	X							
Physical Examination	X							
Labs: Serum Pregnancy Test (if needed)	X							
Urine Pregnancy Test (if needed)	X							
Height		X	X	X	X	X	X	X
Weight		X	X	X	X	X	X	X
Vital Signs		X	X	X	X	X	X	X
Labs: CBC/Metabolic Panel, Hormones,		X	X	X	X	X	X	X

Hemoglobin a1c, TSH, lipids							
Body Composition BIA		X	X	X	X	X	X
Liver Stiffness Fibroscan		X	X	X	X	X	X
Product Dispensing		X	X	X	X	X	X
Stool collection		X	X	X	X	X	X
Satiety Scale		X	X	X	X	X	X

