Secondary Statistical Analyses: All analyses will be performed using SAS software (SAS Institute Inc., Cary, NC). First, linear mixed-effects regression model (or GEE model) will be constructed to examine the study effect on the weight loss over time among the two diet plans, referred to as Model 1. Covariates include gender, diet group (high-protein and standard), time that the measurement is taken, and an interaction between diet plan and time. Models also include the subject-level random effects to account for the correlation between repeated measures at baseline and subsequent follow-up visits occurring at 2 week to 1 month intervals. Next, mixed-effects regression models will be used to evaluate the differences in hormonal patterns among the three diet plans for various hormones of interest (e.g., CCK, GLP-1, etc). Since the hormonal level over time is expected to be nonlinear, the covariates in the model include diet group (normal vs. high-protein), time (in days), and smooth-spline function of time by group interaction. Next, we will also construct linear mixed-effects regression models to examine the study effect on the continuous efficacy variables and safety variables (e.g., vital signs) over time among the three diet plans using PROC MIXED. The continuous efficacy variables include nutritional assessments (FFQ, 3DFR, and Satiety), selected laboratory and biochemical variables (e.g., HbA1c, insulin), body fat, etc. Models include the same fixed effects in Model 1, and the subject-level random effects, which account for the correlation between repeated measures at baseline and pre-defined time points for different variables (e.g.,

baseline and at weeks 2, 4, 6, 8, 12 and 16 for the nutritional assessments). Lastly, generalized linear mixed-effect regressions will be used to model *any* dichotomous and categorical (e.g., severity of adverse events) secondary variables, respectively, in the PROC GLIMMIX or GENMOD. All tests will be two-sided, and significance level is $p < 0.05$.

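### Aim 1's hormone claim has no key hormone and no multiplicity rule: seven readouts each tested at 0.05 carry an 18–30% chance of at least one false positive

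*Combined protocol and SAP*

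**What the plan says.** Section 1.C words Aim 1 as "To Confirm the Hypothesis that a High Protein Diet Reduces Body Weight and Alters the Pattern of Postprandial Gut Hormone Release in Obese Patients". The rationale under that aim lists ghrelin, its ratio to des-acyl ghrelin, and then "anorexigenic peptides PYY, leptin, CCK, GLP-1 and nesfatin-1 following high protein meal ingestion", which makes seven readouts. The assessment list in section 4 (Aim 1, Study Visits) gives, under fasting labs, a "hormone panel (leptin, CCK, GLP-1, PYY, ghrelin, insulin, nesfatin-1"). That is also seven, but with insulin and without the ghrelin ratio.

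Secondary Statistical Analyses (section 4, Aim 1) states that "mixed-effects regression models will be used to evaluate the differences in hormonal patterns among the three diet plans for various hormones of interest", with CCK and GLP-1 given only as examples. The model terms are "diet group (normal vs. high-protein), time (in days), and smooth-spline function of time by group interaction". The section closes with "All tests will be two-sided, and significance level is" p<0.05. No hormone is singled out, no number of positive hormones is set as the criterion for the aim, and no adjustment across hormones is mentioned. Aim 2.1, by contrast, corrects its tests of microbial abundance for multiplicity.

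Weight loss is the only primary endpoint. Section 4 ranks the hormone responses third, and Secondary Endpoints includes hormone levels. The analysis sentence speaks of three diet plans although the trial has two arms; that needs correcting but does not drive this point.

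**The concern.** An aim worded as confirmation needs a rule, set in advance, for what result would confirm it. Here each hormone gets its own test at the full 0.05, and the plan does not separate a positive aim from one chance finding among several. Because the list is open, the hormones that are reported could also be chosen after the data are seen. The section on Hormonal and Biochemical Assays adds to this: a chip with 36 to 40 capture antibodies is read first, and the markers that appear to move go on to quantification by ELISA. What is at stake is the hormone half of the Aim 1 statement, and any account of the diet's effect on satiety that is built on it.

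**Working it through.** **The plan's own figure.** The documents give no power and no family-wise error rate for hormones. Their one sample-size calculation is for weight: 165 evaluable, 55 per arm, effect size 0.245, 80% power. Noncentral F power for three groups of 55 at f = 0.245 and alpha 0.05 is 80.4%, so that figure reproduces as a three-group calculation. Read as two equal arms, f = 0.245 is a standardized difference of 2 × 0.245 = 0.49 SD, which is used below only as a benchmark.

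**Inputs**
- Per-test level 0.05, two-sided (Secondary Statistical Analyses).
- Seven readouts (Aim 1 rationale; the visit panel also has seven).
- About 80 completers per arm (Aim 2.1, Expected results).
- Assumed: one diet-by-time test per hormone, and pairwise correlations between hormone test statistics of 0 to 0.7. The documents give no correlations, so a range is shown.

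**Step 1. Independent tests, no true effect.** P(at least one p<0.05) = 1 − 0.95^7 = 1 − 0.698 = 30.2%. The expected number of false positives is 7 × 0.05 = 0.35.

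**Step 2. Correlated tests.** 400,000 simulated sets of seven equally correlated normal statistics give:

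| Assumed correlation | P(at least one p<0.05) |
|---|---|
| 0.2 | 28.7% |
| 0.3 | 27.1% |
| 0.5 | 23.0% |
| 0.7 | 18.0% |

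Testing the group term as well as the group-by-time term would give further chances of a false positive.

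**Step 3. With the adjustment.** At 0.05/7 = 0.0071 for the smallest p-value, independence gives 1 − (1 − 0.05/7)^7 = 4.9%.

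**Step 4. Cost, single contrast, normal approximation, 80 per arm.** The standard error in SD units is √(2/80) = 0.158.
- Detectable difference at 80% power: (1.960 + 0.842) × 0.158 = 0.44 SD at 0.05, and (2.690 + 0.842) × 0.158 = 0.56 SD at 0.05/7.
- Power at 0.49 SD: 0.49/0.158 = 3.10. At 0.05, Φ(3.10 − 1.96) = 87%. At 0.05/7, Φ(3.10 − 2.69) = 66%.
- Evaluable subjects per arm for 80% power at 0.49 SD: 66 at 0.05, and 104 at 0.05/7.

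Holm's later thresholds are less strict than the first, so the figures at 0.05/7 are the worst case.

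**The case against.** The hormones are not primary. Section 4 places them third, lists them among the secondary endpoints, and words the aim as a test of the hypothesis, not a confirmation of it. Unadjusted testing of secondary endpoints is common when they are read as supportive. Nor does any sentence say that one significant hormone would establish the aim. The 30% figure is also the upper end for seven tests, because leptin and insulin at least should move together.

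Much of this stands. The type I error of the weight comparison is untouched, and the lower figures in Step 2 deserve equal weight. But section 1.C does use the language of confirmation, and the analysis section supplies neither a decision rule nor an exploratory label. Even at a correlation of 0.7, the chance of a false positive is more than three times the nominal 5%. The plan already accepts multiplicity control in Aim 2.1, so asking for it here is no new standard.

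The larger counts should not be pressed. A reader might take the 36 to 40 chip antibodies as the number of tests, but the chip is a screening step and the plan does not say that each antibody gets its own model.

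**Conclusion.** The point holds as a gap in the testing rule for a secondary claim that is worded as confirmatory. With seven readouts and one test each, the chance of at least one false positive is 30% if independent and 18–29% at assumed correlations of 0.7 to 0.2.

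A reader might go further and infer that any hormone difference would merely reflect weight loss, so that the hormone comparison is invalid. The documents do not support that. In a randomized comparison, a difference that arises through weight loss is still an effect of the assigned diet. The route also needs the arms to differ in weight loss. Take the hormone difference as r times the standardized weight difference, with r assumed at 0.3 to 0.7 and 80 per arm. A hormone with no diet effect of its own then reaches p<0.05 with probability 15–58% if the arms differ by 0.49 SD. At the non-diabetic pilot's gap (11.9 − 11.1 = 0.8 lb, or 0.08 SD on the plan's SD of 10 lb) the probability is only 5–6%.

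What remains is a limit on interpretation. The background says of ghrelin that "levels are increased in both obese patients who have lost weight through dietary restriction and patients with anorexia nervosa", and also that "Leptin and insulin are increased in direct proportion to the amount of body fat". Later differences in these three hormones may therefore partly follow weight loss and do not by themselves show the satiety mechanism. For ghrelin, which the plan expects to be inhibited, greater weight loss on high protein would work against the predicted direction.

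**What to change.** In Secondary Statistical Analyses:

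1. Replace the open list with a fixed one. The two seven-item lists differ (insulin in one, the ghrelin ratio in the other), so the plan must choose. It should also say for each readout whether the fasting or the post-meal value is tested, because the aim concerns release after meals while the visit panel sits under fasting labs.
2. Specify one diet-by-time test per hormone.
3. Apply Holm across the list, or the adjustment used in Aim 2.1, naming the method because the Aim 2.1 text does not. The alternative is to make ghrelin, the only hormone with a predicted direction, the single key test at 0.05.
4. Label all other analytes exploratory.
5. State the interpretive limit on later leptin, insulin and ghrelin differences.

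This changes wording only and needs no new data. With Holm, the price is the loss of power in Step 4. The single-key-test option loses no power for ghrelin, but leaves the other hormones without a confirmatory claim.
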